STUDY PROTOCOL PLAN AND STADISTICAL ANALYSIS PLAN (SAP)

UNIVERSITY CEU CARDENAL HERRERA

Principal investigator: [name] [name]

TITLE: Second-generation Radiofrequency Application and Specific Therapeutic Exercise as a Treatment for Stress Urinary Incontinence Due to Urethral Instability. Randomised Clinical Trial

Research and Ethics Committee of CARDENAL HERRERA CEU UNIVERSITY:
CEEI25/646

NCT ID:

DATE: 01-14-2026

STUDY PROTOCOL PLAN

Objectives:

The objectives of our study have been the following:

The purpose of this study is to evaluate the correlation between urethral instability, assessed by ultrasound analysis of the bladder neck opening, and the severity of SUI, assessed by validated standard questionnaires. The determination of standard ultrasound parameters that allow urethral instability to be related to the severity of SUI would be a valuable finding for accurately diagnosing the severity of SUI using low-cost, easy-to-use imaging methods.

A randomized, single-blind clinical trial will be conducted in women with stress urinary incontinence (SUI). Participants will be randomly assigned to one of three intervention groups: radiofrequency (RF), specific pelvic floor muscle exercise (PFMT), or combined treatment (RF + PFMT). The study will be carried out at Clínica Traña (San José, Costa Rica), with an expected start date in 2025. The study will adhere to the principles of the Declaration of Helsinki and current European data protection regulations.

Adult women with urinary leakage and a bladder neck opening greater than 90°, assessed by functional ultrasound, will be included. Women with other pelvic floor disorders, pregnancy, recent treatments (RF, PFME, hormonal or laser therapies), relevant neurological, metabolic, or cardiovascular conditions, prior pelvic surgery, active infections, or contraindications to the interventions will be excluded. The estimated sample size is 117 participants (39 per group), calculated to detect statistically significant differences with 80% power and a 5% significance level, allowing for a 30% dropout rate.

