Before the intervention, all participants will undergo physical examination, digital palpation, and functional pelvic floor ultrasound, as well as complete validated questionnaires assessing urinary incontinence severity and quality of life (ICIQ-SF, King's Health Questionnaire, and Sandvik Severity Index). These assessments will be repeated at the end of the intervention and at 15 days, 3 months, 6 months, and 12 months post-intervention.

Randomization will be performed using statistical software, and outcome assessors will remain blinded to group allocation. Data will be coded and securely stored, ensuring participant confidentiality in accordance with the General Data Protection Regulation (EU 2016/679).

The RF intervention will consist of five weekly sessions of non-ablative fractional vaginal radiofrequency with temperature control and standardized parameters. The PFME program will comprise a structured core and pelvic floor exercise protocol supervised by physiotherapists, conducted twice weekly over a 16-week period. The combined group will receive both interventions.

Primary outcomes will include pelvic floor muscle strength and function (Oxford scale, endurance, and fatigability), ultrasound parameters (bladder neck opening, urethral hypermobility, and presence of prolapse), and validated questionnaires assessing urinary incontinence severity and quality of life.

Statistical Analysis Plan (SAP)

Data will be expressed as mean \pm standard deviation or as a percentage. The distribution of the sample will be determined using the Kolmogorov-Smirnov test. For quantitative variables, depending on the type of variable, Student's t-test or Mann-Whitney U test will be performed. The correlation between variables will be analyzed using Spearman's correlation. In the case of qualitative variables, the association between variables will be analyzed using bivariate or multivariate logistic regression, as appropriate, and contingency tables. The statistical significance of the difference between them will be evaluated using Pearson's χ^2 test. Statistical significance will be assumed with p-values <0.05 .

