To evaluate the diagnostic capacity of bladder neck opening measured by ultrasound analysis in the classification of the severity of stress urinary incontinence, a logistic regression analysis was performed. The dichotomized severity of the Sandvick test (mild/moderate versus severe/very severe) will be taken as the gold standard. Demographic and clinical variables will be evaluated as possible covariates and included in subsequent models if they had a p-value < 0.200 .

Sensitivity, specificity, Youden's index (sensitivity + specificity - 1), and positive and negative likelihood ratios (LR+ and LR-) will be calculated for bladder neck opening at rest, during the Valsalva maneuver, the variation between the two, and for the maximum model with the three variables.

The optimal cutoff point for bladder neck opening at rest will be determined using the Youden index. Subsequently, this value will be transformed into clinical units (mm) by algebraic solving of the logistic model equation, adjusted for relevant covariates (age and BMI). This approach preserves the statistical fit of the model while providing a clinically interpretable threshold.

Studentized residuals, leverage values, and Cook's distances will be estimated to identify possible outliers and influential values in the dependent variable, the predictors, and the model as a whole.

Receiver operating characteristic (ROC) curves will be constructed to determine the area under the curve (AUC). Likewise, the Hosmer-Lemeshow goodness-of-fit test will be applied to compare the observed and expected frequencies of the model (considering $p > 0.05$ as an adequate fit). The accuracy of the probabilistic predictions will be evaluated using the Brier Score (lower values indicate better performance). The

analysis will be performed using SPSS Statistics 29.0 (IBM Corp.)

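### The stated 5% level and 80% power attach to no hypothesis in the randomised comparison: several primary outcomes, three arms and five visits, with no primary outcome, contrast, visit or multiplicity rule

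*Combined protocol and SAP*

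**What the plan says.** The Study Protocol Plan randomises women to radiofrequency, pelvic floor exercise or both. It gives 117 participants, 39 per arm, for 80% power at a 5% level with 30% dropout, without naming the outcome, comparison, visit, effect size or SD behind that figure.

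On outcomes it says "Primary outcomes will include pelvic floor muscle strength and function (Oxford scale, endurance, and fatigability), ultrasound parameters". The ultrasound group has three members (bladder neck opening, hypermobility of the urethra, prolapse). The questionnaires follow without being named again; the assessment paragraph gives them as "ICIQ-SF, King's Health Questionnaire, and Sandvik Severity Index". On timing: "These assessments will be repeated at the end of the intervention and at 15 days, 3 months, 6 months, and 12 months post-intervention".

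The first paragraph of the SAP says that for quantitative variables, "depending on the type of variable, Student's t-test or Mann-Whitney U test will be performed". It then says "In the case of qualitative variables, the association between variables will be analyzed using bivariate or multivariate logistic regression", together with contingency tables and Pearson's chi-square. Its general rule is "Statistical significance will be assumed with p-values <0.05". The rest of the SAP concerns the diagnostic model, where "The dichotomized severity of the Sandvick test (mild/moderate versus severe/very severe) will be taken as the gold standard".

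**The concern.** A three-arm trial offers three pairwise contrasts. With at least six primary measures and five follow-up visits, a claim that one treatment works better could come from many combinations of outcome, pair and visit. The plan does not say which of them is the confirmatory test, and it has no rule limiting the error across them. Student's t and Mann-Whitney each compare two groups, and no three-group test is named for quantitative outcomes. A chi-square test can take a three-arm table, but the SAP does not say that treatment arm is the factor.

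Two things are at stake. The 5% level and 80% power cannot be read as properties of any particular treatment comparison. And the choice of result to emphasise stays open until the data are known, which no later analysis can repair.

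**Working it through.** **Inputs from the Study Protocol Plan.** 39 per arm, three arms, 30% dropout, 80% power, 5% level (sidedness not stated; two-sided assumed). Outcomes: 3 muscle + 3 ultrasound = 6; with three questionnaires, 9. Five post-baseline visits.

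**Assumed, because the documents give no values.** Arms compared pairwise; normal outcomes; equal correlation between outcomes of 0.3 to 0.7; equivalent treatments.

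**The plan's own figure.** 3 × 39 = 117. The 39 is consistent with 27 completers (27/0.7 = 38.6, rounded up to 39) or with 30 (30 × 1.3 = 39). Neither count can be derived, since no effect or SD is stated. Back-solving for one two-sided test with 80% power: d = (1.960 + 0.842) × √(2/n), which is 0.76 for n = 27 and 0.72 for n = 30. With the t distribution these become 0.78 and 0.74.

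**One outcome, one visit, three pairs.** If the tests were independent: 1 − 0.95³ = 0.143. The pairs share arms, so the true value is lower: simulated 0.123 with 27 or 30 per arm. No correlation between outcomes enters this figure.

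**Several outcomes, one visit.** Simulated chance of at least one p<0.05 among the three pairwise t-tests per outcome, 27 per arm:

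| Outcomes | r = 0.3 | r = 0.5 | r = 0.7 |
|---|---|---|---|
| 6 quantitative | 0.502 | 0.436 | 0.359 |
| 9 quantitative | 0.627 | 0.541 | 0.425 |
| 5 quantitative + 4 qualitative | 0.534 | 0.471 | 0.393 |

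The last row treats Oxford grade, hypermobility, prolapse and Sandvik as qualitative, with one three-arm chi-square each and assumed category shares. With 30 per arm, the first two rows change by at most 0.004.

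**All five visits as well.** With outcome/visit correlations from 0.7/0.8 to 0.3/0.6: 0.671 to 0.906 for six outcomes, 0.743 to 0.971 for nine. These values move with the assumptions: for nine outcomes, 0.1/0.3 gives about 99% and 0.8/0.9 about 57%.

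**Procedures that would control the error for one outcome at one visit, 27 per arm.** An overall F test at 5%, with the pairs tested only if it is significant, has familywise error 0.051 when all arms are equal and 0.049 when one differs. Kruskal-Wallis followed by Mann-Whitney gives 0.051 and 0.048. Power of the F-gated procedure for a pair differing by the back-solved d is 0.756 if the third arm equals one of that pair and 0.696 if it lies midway (0.758 and 0.694 with 30 per arm). Bonferroni over three pairs gives 0.65.

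**The case against.** The strongest reply is that the SAP never commits to pairwise comparison of the arms. The objectives open with "The purpose of this study is to evaluate the correlation between urethral instability", and the only two-group split defined anywhere is Sandvik severity, so the two-sample tests may be meant for the diagnostic aim. That stands, and it makes the error rates conditional. A reader might infer that the plan commits the trial to unadjusted pairwise testing; the text does not say so. But the reply does not rescue the plan: on that reading the quantitative comparison between randomised arms has no specified test at all.

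A reader might also infer that 9 × 3 × 5 = 135 tests are planned, with a false positive nearly certain. The plan does not list that cross-product, and the five-visit percentages are illustrations under assumed correlations, not an upper bound.

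If the outcomes were co-primary and all had to succeed, no adjustment across outcomes would be needed. That is a valid design, but no such rule is written.

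Nor do the documents show that 117 is wrong. It cannot be checked, because the inputs behind it are not reported.

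**Conclusion.** The concern holds and should be settled before any between-group results are seen. The firm part needs no simulation: the randomised comparison has no primary outcome, contrast, visit, three-arm test, testing order or adjustment, so its stated level and power refer to no hypothesis.

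The size is conditional on pairwise testing at p<0.05. About 12% for one outcome at one visit needs no assumption about correlation between outcomes. At one visit, 36-50% for six quantitative outcomes and 43-63% for nine rest on 27 completers per arm, normal data and outcome correlation between 0.7 and 0.3. Testing every visit raises the risk further; 67-97% is illustrative only. The p<0.200 covariate rule and the Hosmer-Lemeshow criterion belong to the diagnostic model and do not bear on this point.

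**What to change.** Amend the protocol and SAP before between-group results are seen:

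1. Name one primary outcome at one visit (the sponsor's choice), or else a fixed testing order, or co-primary outcomes that must all succeed. State how baseline is handled (follow-up value, change, or follow-up adjusted for baseline). Make everything else secondary. Say how the visit is timed in each arm: visits count from the end of interventions lasting five weekly sessions in one arm and 16 weeks in another, so the same label can mean different times since randomisation.
2. Prespecify either one primary contrast at 5%, or one three-arm test at 5% (ANOVA/ANCOVA or Kruskal-Wallis) with the three pairs tested at 5% each only if it is significant.
3. Report other outcomes and visits as estimates with confidence intervals, or with Holm adjustment over a stated family.
4. Restate the power for the chosen procedure, with its outcome, effect size and SD.

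The cost is an amendment and fewer confirmatory claims. At the back-solved effect (d about 0.78 with 27 completers per arm, 0.74 with 30), one contrast keeps 80% power with 117 randomised, and the other pairs become secondary. The gated three-arm procedure gives about 70-76% for a pair differing by that effect, and less for pairs that differ by less. No extra patients are needed if that power is stated and accepted. Restoring 80% for such a pair would take about 129 to 150 randomised: 30 or 34 completers per arm divided by 0.7 gives 43 or 49 (129 or 147 in total); 33 or 38 times 1.3 gives 43 or 50 (129 or 150).

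### Pelvic floor muscle measures are primary on equal footing with incontinence severity, although two arms train the pelvic floor and none is described as doing so under RF alone

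*Combined protocol and SAP*

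**What the plan says.** The treatment purpose comes from the title: "Specific Therapeutic Exercise as a Treatment for Stress Urinary Incontinence Due to Urethral Instability". The opening objective of the Study Protocol Plan concerns the correlation between bladder neck opening and severity. No comparative hypothesis between arms is written down.

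On the arms: "Participants will be randomly assigned to one of three intervention groups: radiofrequency (RF), specific pelvic floor muscle exercise (PFMT), or combined treatment (RF + PFMT". On exercise: "The PFME program will comprise a structured core and pelvic floor exercise protocol supervised by physiotherapists, conducted twice weekly over a 16-week period". On the third arm: "The combined group will receive both interventions". The RF arm is described as five weekly RF sessions, with no exercise component mentioned.

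The primary outcomes are three groups in one sentence:

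- The first group is muscle performance: "Primary outcomes will include pelvic floor muscle strength and function (Oxford scale, endurance, and fatigability"
- The second group is imaging: "ultrasound parameters (bladder neck opening, urethral hypermobility, and presence of prolapse"
- The third group is patient-reported: "validated questionnaires assessing urinary incontinence severity and quality of life", the named instruments being "ICIQ-SF, King's Health Questionnaire, and Sandvik Severity Index"

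The sentence sets no order among them. The Statistical Analysis Plan (SAP) adds Student's t or Mann-Whitney tests for quantitative variables and a 0.05 threshold. It names no governing endpoint, hierarchy, co-primary requirement or between-arm contrast.

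**The concern.** Oxford grade, endurance and fatigability describe how well a woman contracts her pelvic floor; they do not measure leakage. Two arms train that function under supervision, and the third, as described, does not. When RF is compared with either exercise-containing arm, a difference on these measures is first of all evidence that training was received and had its direct effect. Whether incontinence improved is a separate question.

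Because these measures have the same primary status as the severity questionnaires, a report could rest a claim that exercise is better than RF on strength alone. A multiplicity correction would not solve this. The strength difference may be entirely real and survive any adjustment, yet still say nothing direct about the condition being treated. What is at stake is the meaning of a positive primary result in the RF-versus-exercise and RF-versus-combined comparisons.

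**Working it through.** **Exposure to training.** Exercise sessions: 2 per week × 16 weeks = 32, in the exercise and combined arms. RF arm: five RF sessions and no exercise described.

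**The plan's own figure.** 3 × 39 = 117, as stated in the Study Protocol Plan. The 39 cannot be derived, because no effect size, SD, sizing endpoint or sidedness is given. Two routes lead to it:

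- 27 / (1 − 0.30) = 38.6, rounded up to 39. By the normal approximation this implies d = (1.960 + 0.842) × √(2/27) ≈ 0.76 for a two-sided pairwise comparison at 80% power.
- 30 × 1.30 = 39, which implies d = (1.960 + 0.842) × √(2/30) ≈ 0.72.

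Neither route shows which outcome the trial was sized for.

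**Completers.** 39 × 0.70 = 27.3, taken as 27 per arm.

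**Chance of p<0.05 on one muscle measure, exercise versus RF.** Two-sided 5% t-test, 2 × 27 − 2 = 52 degrees of freedom, critical value 2.007, non-centrality d × √(27/2) = 3.674 × d. The values of d are assumptions.

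| Assumed d (strength) | Non-centrality | Chance of p<0.05 |
|---|---|---|
| 0.3 | 1.10 | 19% |
| 0.5 | 1.84 | 44% |
| 0.8 | 2.94 | 82% |
| 1.0 | 3.67 | 95% |

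**At least one of the three muscle measures.** This assumes the same d on each and a correlation between measures from 0.8 down to 0 (simulation, normal approximation). The chance of at least one significant result in favour of exercise is 60% to 84% at d = 0.5, and 92% to 99.6% at d = 0.8.

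**If one severity score had to show the effect.** Suppose there is no true difference in severity. For one contrast at one time point, the chance of significance in favour of exercise on that score is 2.5%, half of the two-sided 5%. Requiring it therefore caps the chance of an exercise-over-RF efficacy claim at 2.5%, however large the strength effect.

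The two kinds of percentage must not be read as like against like. The table gives power for a true difference in one quantity; the 2.5% is an error rate for another. Set side by side, they show only that strength can be significant for reasons unrelated to leakage.

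**The case against.** The strongest reply is that the plan contains no success rule. It does not say that one primary outcome suffices, and it names no contrast. A reader might infer that a significant Oxford result is, as the plan stands, a primary success for exercise. The text does not go that far; it only fails to rule this out. This stands, and the point is worded accordingly.

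Second, the severity questionnaires are themselves primary, so a null leakage result would be reported at the same level. This also stands. Symptoms are measured; what is missing is any statement that they govern the conclusion.

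Third, a reader might infer that a strength difference is nearly guaranteed. That depends on a d of 0.8 or more, which the documents do not supply; at 0.3 the chance is 19%. Follow-up runs to 12 months after the intervention, and a training effect may fade by the later visits. The Oxford scale is ordinal and the SAP allows Mann-Whitney, so the t-test figures are approximate.

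Fourth, combined versus exercise alone holds exercise constant. The imbalance does not arise there, and the documents give no basis for saying that the muscle measures are uninformative about what RF adds.

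Fifth, muscle function is a legitimate outcome in a trial of pelvic floor exercise. Agreed, as a mechanism. That supports measuring it, but not letting it carry a claim about incontinence. Assessor blinding limits rating bias and does not change what the scale measures.

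**Conclusion.** The point holds in a limited form. The plan allows a strength difference between exercise and RF to be reported as a primary result with no difference in leakage severity, because the primary outcomes are unranked and no incontinence effect is required. It does not direct that conclusion.

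The size depends on an effect that the documents do not give, so the full range applies: from about one trial in five at d = 0.3 to 19 in 20 at d = 1.0, for one muscle measure with 27 completers per arm. The conclusion itself rests on the outcome list and the absence of a governing rule, and would be the same for any d above zero. It covers the two comparisons of RF with an exercise-containing arm.

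This should be changed, but it does not invalidate the trial, since incontinence severity is already collected as a primary outcome.

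**What to change.** In the Study Protocol Plan, reclassify Oxford grade, endurance and fatigability as secondary mechanistic outcomes. In both the Study Protocol Plan and the SAP, state that conclusions on the relative efficacy of RF, exercise and combined treatment rest on one prespecified incontinence severity questionnaire score already being collected (for example ICIQ-SF), at a named time point.

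List bladder neck opening and the other ultrasound parameters as supporting evidence. They should not be an alternative basis for efficacy, because an imaging difference without a change in leakage would raise the same problem. Report quality of life alongside.

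The cost is wording only: every measurement and visit stays. The sponsor gives up a possible significant primary result on strength.

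### The SAP does not say how the Kolmogorov-Smirnov result and variable type decide between t-test and Mann-Whitney, so the test and its estimand can change between visits

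*Combined protocol and SAP*

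**What the plan says.** The first paragraph of the section Statistical Analysis Plan (SAP) contains the whole plan for comparing quantitative outcomes. It says "The distribution of the sample will be determined using the Kolmogorov-Smirnov test" and continues: "For quantitative variables, depending on the type of variable, Student's t-test or Mann-Whitney U test will be performed". The same paragraph begins "Data will be expressed as mean" with standard deviation, or percentages, and gives no other summary for variables that end up with a rank test. The threshold is "Statistical significance will be assumed with p-values <0.05".

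The Study Protocol Plan says that the assessments made before the intervention are "repeated at the end of the intervention and at 15 days, 3 months, 6 months, and 12 months post-intervention", which is five post-baseline time points. The primary outcomes are of mixed type: Oxford grade, endurance and fatigability, ultrasound parameters and questionnaires.

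The SAP does not state:
- which outcome gets which test;
- whether the Kolmogorov-Smirnov (KS) test is run per visit, per arm, pooled, or once per variable;
- whether the Lilliefors correction is used, and at what threshold;
- what happens when arms or visits disagree;
- any effect measure or confidence interval for the comparison of arms.

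**The concern.** The KS sentence comes directly before the choice of test, and the SAP gives the KS result no other use: correlations are already fixed as Spearman and summaries as mean with SD. The natural reading is therefore that normality steers the choice.

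A t-test compares means, while Mann-Whitney compares the ordering of values in two groups. If normality is tested afresh at each visit, a questionnaire score could be reported as a mean difference at 3 months and as a rank comparison at 6 months, although its true distribution had not changed. There would then be no single treatment effect to describe over 12 months, and means with SDs could stand beside p-values that do not test means. Because no outcome is tied to a test beforehand, the analyst also has a choice to make after seeing the data.

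**Working it through.** **Inputs from the documents.** Three arms of 39 women, sized "with 80% power and a 5% significance level, allowing for a 30% dropout rate"; five post-baseline assessments; a significance level of 0.05. Evaluable women per arm after dropout: 39 × (1 − 0.30) = 27.3, taken as 27. The plan gives no figure of its own for how often each test would be used, so there is none to reproduce.

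**Assumptions, not in the documents.** Gamma-shaped scores with skewness 0.7, 1.0 or 1.4 (shape 8, 4 or 2; skewness = 2/√shape); the same true shape at every visit; between-visit correlation 0.6; one pair of arms; KS at 0.05 in each arm at each visit; Mann-Whitney if either arm fails. A trial counts as mixed when the chosen test is not the same at all five visits.

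**Step 1: hand check with normal data.** With the Lilliefors correction each arm fails 5% of the time. At one visit, P(Mann-Whitney) = 1 − 0.95² = 0.0975. Treating visits as independent, P(mixed) = 1 − 0.9025⁵ − 0.0975⁵ = 1 − 0.599 − 0.000 = 0.40. Simulation with correlated visits also gives about 40%. So switching occurs even when every score is exactly normal.

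**Step 2: skewed data.**

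| Setting | Mann-Whitney chosen, 27 / 39 per arm | Mixed trials |
|---|---|---|
| Lilliefors KS, skewness 1.0 | 42% / 53% of visits | about 90% |
| Lilliefors KS, skewness 0.7–1.4 | – | about 59–90% |
| Uncorrected KS, skewness 1.0 | – | 4% (27) / 10% (39) |
| Uncorrected KS, skewness 0.7–1.4 | – | about 1–35% |
| KS once per variable | – | 0% by construction |

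The independence formula at 42% gives 1 − 0.58⁵ − 0.42⁵ = 1 − 0.066 − 0.013 = 0.92. The simulated figure is slightly lower because visits are correlated. The 59% end belongs to the strongest skew with 39 per arm, where KS rejects at most visits and Mann-Whitney is chosen fairly consistently. For uncorrected KS the upper end is about 28% with the large-sample critical value and about 35% with the exact one.

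**Step 3: other shapes.** These runs apply KS once per visit to a single sample of 27 or to 81 pooled, with correlation 0.5.

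| Assumed shape, Lilliefors KS | Mixed, n = 27 | Mixed, n = 81 |
|---|---|---|
| Lognormal, σ 0.3 | 63% | 91% |
| Lognormal, σ 0.5 | 90% | 42% |
| 0–21 integer score | 49–52% | 89–94% |
| Coarse 0–5 scale | 9% | 0% |

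On the coarse scale KS rejects almost every time, so the choice hardly varies.

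**Step 4: error rate.** With 27 per arm and no true difference, the rule followed mechanically rejects in 5.25% of trials (normal) and 5.0% (lognormal, σ 0.5). Across the gamma settings the range was 4.1–6.0%, with Monte Carlo error of about 0.4 points.

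Suppose instead that the analyst took whichever test was significant. Then P(either < 0.05) = ½ × (P(t) + P(MW) + P(the two disagree)):
- normal: ½ × (0.0525 + 0.0500 + 0.0198) = 0.061;
- lognormal, σ 0.5: ½ × (0.0472 + 0.0453 + 0.0348) = 0.064.

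For a single comparison, free choice between these two tests therefore costs about one percentage point.

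**The case against.** The strongest reply is that the SAP's stated criterion is variable type, not the normality result. On that reading continuous measures such as bladder neck opening would get the t-test and ordinal ones such as Oxford grade would get Mann-Whitney, and nothing could switch between visits. The wording permits this, so a reader who infers that the plan makes the test change from visit to visit goes beyond the text: neither a KS-driven rule nor visit-by-visit testing is stated. What remains is that this reading leaves the KS test without a function, and no variable is classified by type. The test is not pre-specified on either reading.

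Second, the large percentages depend on the Lilliefors correction and on an either-arm rule, neither of which is in the SAP. This stands, and is why the uncorrected results are shown beside them.

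Third, a reader might infer that choosing the test from the data inflates the false-positive rate. The calculations do not support that: the two-stage rule stays near 5%, and the two tests agree in about 97–98% of trials without a true difference.

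Fourth, deleting the KS step would not by itself supply a coherent estimate over time, because the SAP names no longitudinal model, effect measure or interval. This also stands, and the remedy has to fill that gap. That both named tests compare two groups while the trial has three arms is a separate matter.

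**Conclusion.** The point holds as a gap in specification. The SAP does not say how the KS result and variable type together select the test, or at what level KS is applied. If KS decides per visit, the test and what it estimates can change by chance over the five follow-up visits. Under that condition and the assumed gamma scores, the frequency runs from about 1% to about 90% of trials, and the KS variant matters most; if KS is run once per variable it is zero. Score shapes, correlation and the either-arm rule are assumptions. The consequence is an unstable estimand and avoidable discretion, with no material type I error inflation shown. This is a low-cost improvement and not a defect that threatens the trial's validity.

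**What to change.** Remove the Kolmogorov-Smirnov test as gatekeeper. Before any comparison of arms, list each outcome with one method and one effect measure with a 95% CI. For example:

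- questionnaire scores and continuous ultrasound measures: a linear mixed model over all post-baseline visits, adjusted for the baseline value, reporting the adjusted mean difference at each visit;
- Oxford grade: an ordinal model with a common odds ratio, or another pre-specified rank-based method with its own effect measure.

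Check residuals afterwards and report any alternative analysis as sensitivity only. These models are one reasonable choice among several; what matters is that the method is fixed per outcome and does not depend on a normality test. Switching is then zero by construction. The baseline values are already collected, so no extra data or participants are needed. The cost is rewording the SAP and slightly more analysis work.
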